### **Exclusion Criteria**

- History of a medically compromised condition and intellectual disability.
- Any allergy to local anesthesia.
- Active pathology at the site of injection.
- Prior history of intra-oral injection.
- Frankl behavior I or II.
- Children/parents not willing to participate in the study.
- Needle phobia.
- Patients require treatment under conscious sedation.

## **C. Sample Size**

Cochrane sample size calculation for detecting a minimum difference of between visual analog score for the study and control groups

$$n = 2 \left( \frac{Z_{1-\alpha/2} + Z_{1-\beta}}{SE} \right)^2$$

Where

$$SE = \frac{\mu_d}{\sigma_d}$$

[figure not shown]
From the study of Lakshimi Lakshmanan and Vignesh Ravindran, the analog score yields the following measures for the study and control groups  $40.66 \pm 14.60$  and  $61.33 \pm 9.73$ , respectively:

[figure not shown]
$\mu_d = 20.67$  and  $\delta d = 12.41$ , the  $SE = 1.67$ , and the different scenarios according to power are as follows:

Power	$\alpha$	$2(z_{1-\alpha/2} + z_{1-\beta})^2$	Sample size
0.95	0.01	31.5	53
	0.05	26	43
0.90	0.01	17.1	29
	0.05	21	35
0.80	0.01	20.1	34
	0.05	12.4	21

With a power of 80% and a significance level of 5%, the minimum sample is 21 children in each arm.

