## **D. Procedure and Indices:**

### **Randomization, Blinding and the procedure with topical anesthesia (EC or BC):**

Pre-local analgesia topical BC or EC technique will be selected randomly and applied per the protocol. A single calibrated operator (A.A) using randomly selected sealed envelopes that have been previously divided equally according to sample size arms. The selected envelope is then opened by the operator, who applies either the EC or BC topical anesthesia technique based on the chosen envelop. Followed by maxillary local analgesia buccal infiltration for a single tooth by a calibrated operator (A.A). The child is then observed and assessed by the blinded primary investigator (N.A) (to the topical anesthesia technique) for pain perception during local anesthesia infiltration based on the Sound, Eye, Motor index used in this study. The child is then asked to rate the Visual Analog Scale and Facial Pain Scale. Heart rate of the patient will be recorded as per below protocol.

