## H. Statistical Analysis

Data will be entered into a computer using SPSS® for windows version 28.0 (SPSS Inc., Chicago, IL). Descriptive statistics will be used to describe categorical and continuous variables by proportion and measure of tendency, and measure of dispersion, respectively. The continuous measurements: score of analog and other variables (H) will be tested for normality using Shapiro Wilk. Comparisons between two arms will be administered on the function of the normality test using Parametric (T-test, chi-square) or non-parametric (Mann-Whitney test or exact fisher test). A P-value of less than 0.05 will be considered significant in all statistical analyses.

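### The sample-size table multiplies by the standardised effect instead of dividing by its square, and four of its six z-factors are wrong, so 21 per arm is not the minimum for 80% power

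*Combined protocol and SAP*

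**What the plan says.** Section C gives the per-arm formula n = 2[(z₁₋α/₂ + z₁₋β)/SE]², with SE defined as the mean difference over the standard deviation. The inputs come from a cited cryotherapy trial, of which the plan says "the analog score yields the following measures for the study and control groups": 40.66 ± 14.60 and 61.33 ± 9.73. From these it takes a difference of 20.67, an SD of 12.41 and SE = 1.67, "and the different scenarios according to power are as follows". A table then lists six combinations of power and α, each with a factor headed as 2(z₁₋α/₂ + z₁₋β)² and a sample size. The conclusion is "With a power of 80% and a significance level of 5%, the minimum sample is 21 children in each arm".

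The null hypothesis is no difference between the two topical agents. Section H (Statistical Analysis) plans a t-test or Mann-Whitney test and states "A P-value of less than 0.05 will be considered significant in all statistical analyses". The randomisation section has envelopes "previously divided equally according to sample size arms", which implies 1:1 allocation.

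**The concern.** The table fails on its face. At 90% power, the stricter α of 0.01 is said to need fewer children (29) than α = 0.05 (35). At α = 0.01, 90% power is said to need fewer children (29) than 80% power (34). Neither is possible for a fixed effect and SD.

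This table is the only justification for the number of children enrolled. If it is wrong, so is the statement of power that would be carried into the trial report. A reader facing a non-significant result would believe that 21 per arm gave 80% power for a difference of about 20 points. The trial can in fact detect a much smaller difference, so the result would be misread.

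**Working it through.** **Inputs** (all from Section C): means 40.66 and 61.33; SDs 14.60 and 9.73; formula as printed, using z₁₋α/₂ and therefore two-sided; 1:1 allocation.

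**Effect size.** The difference is 61.33 − 40.66 = 20.67. The pooled SD is √[(14.60² + 9.73²)/2] = 12.41. The ratio is 20.67/12.41 = 1.666, which the plan rounds to 1.67. These steps reproduce. The ratio is a standardised effect, not a standard error. Its square is 2.774 (2.789 from the rounded 1.67; the rounded-up n is the same with either).

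**The plan's sample sizes.** They are reproduced by multiplying each printed factor by 1.67, and this works in all six rows:

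| Power | α | Printed factor | Printed factor × 1.67 | Printed n | Two-sided 2(z+z)² | One-sided 2(z+z)² | n by the plan's formula (two-sided factor ÷ 2.774) |
|---|---|---|---|---|---|---|---|
| 0.95 | 0.01 | 31.5 | 52.6 | 53 | 35.63 | 31.54 | 12.84 → 13 |
| 0.95 | 0.05 | 26 | 43.4 | 43 | 25.99 | 21.64 | 9.37 → 10 |
| 0.90 | 0.01 | 17.1 | 28.6 | 29 | 29.76 | 26.03 | 10.73 → 11 |
| 0.90 | 0.05 | 21 | 35.1 | 35 | 21.01 | 17.13 | 7.58 → 8 |
| 0.80 | 0.01 | 20.1 | 33.6 | 34 | 23.36 | 20.07 | 8.42 → 9 |
| 0.80 | 0.05 | 12.4 | 20.7 | 21 | 15.70 | 12.37 | 5.66 → 6 |

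**First error.** The formula puts the standardised effect in a squared denominator, but the table multiplies by it once. Under the table's arithmetic, a larger expected effect would call for more children.

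**Second error.** Only the factors 26 and 21 match the two-sided header. The entries 31.5, 20.1 and 12.4 are one-sided values for their own labels. The entry 17.1 stands in an α = 0.01 row but is the one-sided α = 0.05 value for 90% power. For the row the plan relies on, the two-sided factor is 2(1.960 + 0.842)² = 15.70, whereas 2(1.645 + 0.842)² = 12.37.

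**Could another reading give 21?** No variant tried does, for 80% power and α = 0.05:
- One-sided: 12.37/2.774 = 4.46, so 5 per arm.
- Division by 1.67 without squaring: 15.70/1.67 = 9.4, so 10.
- The larger SD, 14.60: 15.70 × (14.60/20.67)² = 7.8, so 8.
- Two-sample t-test solution: 6.77, so 7.
- Mann-Whitney at an assumed worst-case relative efficiency of 0.864: 6.77/0.864 = 7.8, so 8.

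**What 21 per arm delivers.** For the 20.67-point difference, the normal approximation gives 1.666 × √(21/2) − 1.960 = 3.44, a power of about 99.97%. The t-test gives about 99.95%.

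The standardised difference detectable with 80% power (two-sided 5%) is (1.960 + 0.842) × √(2/21) = 0.865 by the normal approximation and 0.886 by t-test. In VAS points at SD 12.41 these are 10.7 and 11.0. For 90% power by t-test it is 1.025 × 12.41 = 12.7. The t-test figure for 80% power changes with the SD and the test:
- SD 14.60 (the larger of the two cited): 0.886 × 14.60 = 12.9.
- SD 20 (an assumption): 0.886 × 20 = 17.7.
- Mann-Whitney at SD 12.41: 11.0/√0.955 = 11.3 if the data are normal, and 11.0/√0.864 = 11.8 at the assumed worst case.

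**The case against.** The strongest reply is that the error is conservative. On the plan's inputs 21 per arm is more than enough, and correcting the table changes no enrolment, endpoint or analysis. That is true, and the point must not be read as saying the sample is too small. It does not rescue the statement, because both the claimed minimum and the claimed power are false.

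A careful reader could work out the detectable difference from the printed n, SD and significance level. That is also true, but the plan tells the reader something different.

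Two cautions about the repair do stand. First, 6 per arm comes from the plan's normal approximation. The planned t-test has only 73.9% power with 6 per arm and 81.6% with 7, so a table showing 6 without comment would again fall short of its label. Second, 11 points is solved backwards from n = 21 and an SD taken from another trial. Nothing in the documents says 11 points matters clinically, so it can describe the sample but cannot justify it.

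How the wrong factors arose is partly inference. The printed 26 also equals the one-sided value for 90% power and α = 0.01 (26.03), so some entries may be displaced. No such reading makes the table correct.

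**Conclusion.** The statement is wrong as written. For a difference of 20.67, SD 12.41, two-sided α = 0.05, 80% power and equal arms, the plan's formula gives 6 per arm and the t-test 7. The printed 21 is 3.5 times the formula's result (21/6) and 3 times the t-test's (21/7). Under the same assumptions 21 per arm has about 99.95% power. Its 80% detectable difference is about 11.0 VAS points at SD 12.41, or 12.9 at SD 14.60.

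The requirement is overstated, so the planned enrolment is adequate for the stated assumptions. Whether a 20.67-point difference seen with cryotherapy is a reasonable expectation for ethyl chloride against benzocaine is a separate question, not settled here.

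**What to change.** In Section C:

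1. Recompute the factor column with z₁₋α/₂ in every row: 35.6, 26.0, 29.8, 21.0, 23.4 and 15.7.
2. Divide by the squared standardised effect, giving 13, 10, 11, 8, 9 and 6 per arm. Label these as normal approximations and state the t-test requirement for the chosen scenario (7 per arm).
3. Rename SE as the standardised effect size.
4. Keep 21 per arm and replace the concluding sentence with text such as: *Twenty-one children per arm give 80% power (two-sided 5%, t-test) to detect a difference of 11 VAS points if the SD is 12.4, or about 13 points if it is 14.6. Power for the 20.67-point difference of the cited cryotherapy trial exceeds 99%.*
5. Present the 11 points as what this sample can detect. If the sponsor has a minimum relevant difference in mind, state it separately with its source.

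The cost is a wording change to one section. Enrolment, procedures and timeline stay as they are.

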**Fig 1: Study Flow Chart**

BC ( Benzocaine gel), EC (Ethyl Chloride), HR (Heart rate), SEM ( Sound, Eye, Motor ) index, VAS (Visual Analog Scale) and F.P (Face Pain scale).

## **D. Procedure and Indices:**

### **Randomization, Blinding and the procedure with topical anesthesia (EC or BC):**

Pre-local analgesia topical BC or EC technique will be selected randomly and applied per the protocol. A single calibrated operator (A.A) using randomly selected sealed envelopes that have been previously divided equally according to sample size arms. The selected envelope is then opened by the operator, who applies either the EC or BC topical anesthesia technique based on the chosen envelop. Followed by maxillary local analgesia buccal infiltration for a single tooth by a calibrated operator (A.A). The child is then observed and assessed by the blinded primary investigator (N.A) (to the topical anesthesia technique) for pain perception during local anesthesia infiltration based on the Sound, Eye, Motor index used in this study. The child is then asked to rate the Visual Analog Scale and Facial Pain Scale. Heart rate of the patient will be recorded as per below protocol.

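### Allocation relies on a draw of unnumbered sealed envelopes opened by the unblinded treating operator, so a discarded or repeated draw would leave no trace

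*Combined protocol and SAP*

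**What the plan says.** Section D (Procedure and Indices) contains the whole description of allocation. The technique is chosen at random, with a single calibrated operator using "randomly selected sealed envelopes that have been previously divided equally according to sample size arms". Then: "The selected envelope is then opened by the operator, who applies either the EC or BC topical anesthesia technique based on the chosen envelop". The injection comes next: "Followed by maxillary local analgesia buccal infiltration for a single tooth by a calibrated operator", with the same initials as the person who handled the envelopes. Only the observer is described as blinded: "The child is then observed and assessed by the blinded primary investigator".

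Section C sets the size: "With a power of 80% and a significance level of 5%, the minimum sample is 21 children in each arm". Section I says that the principal investigator identifies ineligible patients, that a clinical investigator (not further identified) verifies eligibility, and that whoever takes consent does not treat. The Appendix I data sheet has columns for serial number, gender, age, infiltration, group, heart rate and the three pain indices. It has no envelope number and no behaviour grade.

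The documents do not mention a generated sequence, opacity or numbering of the envelopes, an independent preparer or custodian, marking of the envelope before opening, or a log.

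**The concern.** A draw without replacement from an equally divided set is a valid randomisation only if every draw is kept. Here no envelope belongs to a particular child until someone has looked inside it. If the person opening it sets it aside and takes another, the final arm totals still balance and the data sheet looks the same.

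That person is unblinded and gives the treatment, so he or she may form a view of how the child is likely to cope. Both Frankl III and Frankl IV children are eligible under Section B, so behaviour varies among those enrolled, and it plausibly relates to all the pain ratings. The grade is not on the data sheet, so steering by behaviour could be neither seen nor adjusted for. The comparison of the two agents is then open to selection bias in either direction.

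**Working it through.** **Inputs.** From Section C: 21 per arm, SD 12.41, two-sided 5% level, planning difference 20.67. My assumptions: the envelope pool is 21/21 (no envelope count is printed); calmer and more anxious children are present in equal numbers and differ by D = 5 or 10 VAS points (the documents give no figure).

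**The plan's own figures.** The SD reproduces: √((14.60² + 9.73²)/2) = 12.41. The 21 is recovered as 12.4 × 1.67 = 20.7, although the printed formula, with the two-sided multiplier 15.70, gives 15.70/1.67² = 5.6, or 6 per arm. That is a separate matter. The planned 21 is used here only as the size of the pool.

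**Route 1: prediction.** An operator who always guesses the arm with more envelopes left in an n/n pool expects n + 2^(2n−1)/C(2n,n) − ½ correct guesses.
- n = 21: 21 + 4.085 − 0.5 = 24.59 of 42, or 58.5%, against 50% by chance.
- Expected number of final envelopes known for certain: 2n/(n+1) = 42/22 = 1.9.
- Pools of 14 to 30 per arm give 60.2% to 57.3%.

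**Route 2: re-drawing.** If one unwanted envelope can be set aside, the first child gets the preferred arm with probability 1 − (21/42)(20/41) = 75.6%, instead of 50%.

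Bias in the difference between arm means:
- A successful re-draw moves one child to the preferred arm, and the rejected envelope goes to some later child. With an equal mix, that later child is of the opposite type about half the time, so the average bias is about D/21 per re-draw.
- If two children of opposite type are deliberately exchanged, the bias is 2D/21 per pair. This is the upper case.

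The standard error is 12.41 × √(2/21) = 3.83. Type I error is the chance that a noncentral t with 40 df and noncentrality bias/3.83 falls outside ±2.021.

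| Scenario | D | Bias (VAS points) | Bias/SE | Two-sided type I error |
|---|---|---|---|---|
| 3 re-draws | 5 | 3 × 5/21 = 0.71 | 0.19 | 5.4% |
| 3 re-draws | 10 | 3 × 10/21 = 1.43 | 0.37 | 6.5% |
| 3 exchanged pairs | 5 | 6 × 5/21 = 1.43 | 0.37 | 6.5% |
| 3 exchanged pairs | 10 | 6 × 10/21 = 2.86 | 0.75 | 11.3% |

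Against the planning difference of 20.67, these biases are 3.5% (0.71/20.67) to 14% (2.86/20.67).

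**Would small blocks help?** The operator knows past allocations under any scheme. The same formula within a block gives:
- blocks of 4: (2 + 8/6 − 0.5)/4 = 70.8%;
- blocks of 6: (3 + 32/20 − 0.5)/6 = 68.3%;
- blocks of 8: (4 + 128/70 − 0.5)/8 = 66.6%.

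Hiding or varying the block size does not rescue this, because guessing the arm that lags behind needs no knowledge of it. Simulated lists of 42 gave 68.9% for random 4/6 blocks and 67.7% for random 4/6/8 blocks. All exceed the 58.5% of a single unblocked set.

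**The case against.** The best defence is that the plan does randomise, seals the envelopes, keeps consent apart from treatment, screens through the principal investigator and uses a blinded observer for the Sound, Eye, Motor index. Foreseeing the next arm therefore does not clearly let the operator decide who enters. This stands in part: it is why prediction is a minor route, although the clinical investigator who verifies eligibility could be the operator. None of it prevents an opened envelope from being set aside.

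Some stronger readings are tempting, and the documents do not support them:
- **That the operator hand-picks from a fixed 21/21 pool.** Only opening is explicitly assigned to the operator. Drawing by the operator is the natural reading, but that sentence has no main verb. The pool size is inferred from Section C, which calls 21 a minimum. Nor is it stated that the operator sees the child's behaviour before the draw.
- **That type I error reaches about 23%.** That needs five exchanged pairs at D = 10: bias 10 × 10/21 = 4.76, bias/SE 1.24, error 22.8%. It means ten coordinated changes among 42 children, which casual re-drawing does not produce. The eligible range of behaviour is also narrow: Frankl III or IV only, with needle phobia and sedation cases excluded.
- **That no analysis could help.** Adjustment for a recorded baseline behaviour measure could reduce the bias. The data sheet simply has none.

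**Conclusion.** The concern holds as a weakness of the stated allocation method. The unblinded treating operator opens envelopes from an equally divided set, and no stated step would reveal a discarded or repeated draw. A reader might infer that allocation was in fact manipulated; the text supports only that selection bias is possible.

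The likely size is modest. Prediction gives about 58.5% correct guesses, with about the last 2 envelopes certain, if the pool is 21/21 and past draws are remembered. A few re-draws give a bias of roughly 1 to 3 VAS points and a type I error of about 5.4% to 11%. The upper end requires three deliberate exchanges and a 10-point difference between types of child. Both that difference and the number of re-draws are assumptions. The absence of a safeguard rests on the text itself, and the remedy is nearly free, so the change should be made.

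**What to change.** Rewrite the allocation paragraph of Section D as follows.

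1. One computer-generated, unblocked 1:1 list for the planned total, prepared by an existing colleague who does not recruit, treat or assess.
2. Opaque, sealed, sequentially numbered envelopes made up from that list and taken strictly in order.
3. After consent and the eligibility check, and before opening, the child's code and the time are written on the envelope.
4. Every opening is entered in a log, and the envelope number is added to the Appendix I data sheet.
5. A plain statement of who takes and who opens each envelope.

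Do not use small blocks, which make the next arm easier for this operator to predict. Do not make opening depend on the first heart-rate reading: the heart-rate section times it immediately before the injection, which may fall after the topical agent has been applied.

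An unblocked list is as predictable as the present pool. The gain is that a departure from the order becomes visible. The cost is a short preparation time, a few sentences and one extra data field, with no additional children or visits.

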#### **1- Heart rate (HR)**

Physiological changes in HR will be measured in beats per minute (bpm) and registered using a pulse oximeter. Each participant's heart rate will be recorded immediately before and after the injection using an FDA-approved pulse oximeter (SantaMedical SM-165 Fingertip Pulse Oximeter ®, China). The injection site will be dried and isolated using a cotton roll. A small

[figure not shown]
quantity of the topical anesthesia 20% Benzocaine (Dharma Research, Miami, USA®) anesthetic gel will be applied using the end of an applicator stick directly at the site of penetration for 30 s and then left for 1 min to ensure effectiveness. All the time periods will be calculated using the clock App timer available on an iPhone®. The injection of the anesthetic solution is performed according to the standard technique mentioned below. Directly after the injection, the pulse rate will be recorded a second time.

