#### Specific objectives

- To compare the efficacy of BC and EC on buccal infiltration.
- To compare the physiological changes observed during the administration of local anesthesia with two pre-anesthesia topical application techniques (BC and EC).
- To compare the reported and observed pain perception of two topical anesthetic techniques (BC & EC) with different age groups and gender.

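### The heart-rate comparison is undefined and unadjusted, and the first reading is not clearly placed before or after the topical agent

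*Combined protocol and SAP*

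**What the plan says.** **Objective.** One of the specific objectives concerns HR: "To compare the physiological changes observed during the administration of local anesthesia with two pre-anesthesia topical application techniques".

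**Measurement.** The HR subsection of section D opens with "Physiological changes in HR will be measured in beats per minute (bpm) and registered using a pulse oximeter" and then fixes the readings: "heart rate will be recorded immediately before and after the injection using an FDA-approved pulse oximeter". The next step narrated is "The injection site will be dried and isolated using a cotton roll". After that come the BC gel for 30 s, a wait of 1 min, the injection, and finally "Directly after the injection, the pulse rate will be recorded a second time". The ethyl chloride (EC) steps are not described there. Section A describes EC application but gives no HR timing.

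**Allocation.** The randomization paragraph of section D says "The selected envelope is then opened by the operator, who applies either the EC or BC topical anesthesia technique based on the chosen envelop". For HR it only points forward: "Heart rate of the patient will be recorded as per below protocol".

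**Analysis.** Section H covers HR at most through a bracketed letter: "The continuous measurements: score of analog and other variables (H) will be tested for normality using Shapiro Wilk". For continuous data it then offers a t-test or a Mann-Whitney test between arms, chosen by the normality test. It names no post value, change or percent change, and no covariate.

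**Sizing.** Section C sizes the trial on the visual analog score, at 21 children per arm.

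**The concern.** Two readings per child allow at least three between-arm comparisons: the second reading alone, the change, or the second reading adjusted for the first. The objective and the HR subsection both speak of changes, so change is the evident intent. Section H does not say so, and the choice could therefore be made after the data are seen.

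The place of the first reading decides which comparison is sound. If it is taken before the agent, it is a true baseline, and adjusting for it gains precision at almost no cost. If it is taken after the envelope is opened and the agent applied, it is a post-randomisation measurement that the agent itself may have moved. Neither change nor adjustment then has the usual baseline interpretation.

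**Working it through.** **Step 1. When is the first reading?**

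| Evidence in section D | Implied position |
|---|---|
| Wording: immediately before the injection | After the topical agent |
| Narrated order: reading, drying, gel 30 s, wait 1 min, injection, second reading | Before the agent, so at least 30 + 60 = 90 s before the injection in the BC arm |
| Randomization paragraph | No reading point; refers to the HR subsection |

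No sentence in the available text decides between the two.

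**Step 2. Precision if the first reading precedes the agent.**

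Inputs from the plan: 21 per arm (section C), so N = 42; significance level 0.05 (section H), taken as two-sided because the section C formula uses 1 − α/2. The plan gives no figure for HR to reproduce. Assumptions: equal SDs at the two readings, and correlation r between them of 0.3, 0.5, 0.7 or 0.8. The documents give no r.

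Variance of the arm contrast, in units where an unadjusted comparison of the second reading is 1:

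- Change: 2(1 − r)
- ANCOVA: 1 − r²
- Ratio, ANCOVA to change: (1 − r²) / [2(1 − r)] = (1 + r)/2
- Allowing for the estimated slope: multiply by 1 + 1/(N − 4) = 39/38

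A t-test with 21 per arm has 80% power at a standardised difference of 0.886. The difference that change detects, in SDs of HR, is therefore 0.886 × √[2(1 − r)].

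| r | Change 2(1 − r) | ANCOVA 1 − r² | Ratio (1 + r)/2 | Ratio × 39/38 | 42 ÷ that ratio | Difference change detects at 80% power (SD) | ANCOVA power at that difference |
|---|---|---|---|---|---|---|---|
| 0.3 | 1.40 | 0.91 | 0.65 | 0.67 | 63 | 1.05 | 93% |
| 0.5 | 1.00 | 0.75 | 0.75 | 0.77 | 55 | 0.89 | 89% |
| 0.7 | 0.60 | 0.51 | 0.85 | 0.87 | 48 | 0.69 | 85% |
| 0.8 | 0.40 | 0.36 | 0.90 | 0.92 | 45 | 0.56 | 83% |

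The sixth column is the number of children analysed on change that would match 42 analysed by ANCOVA. Simulation of 40,000 trials of 21 v 21 gave variance ratios of 0.66, 0.77, 0.87 and 0.93 and the same powers, with ANCOVA type I error at about 5%.

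The undefined quantity also matters by itself. The second reading alone detects 0.89 SD whatever r is, while change runs from 1.05 to 0.56 SD over this range. Change is the less precise of the two below r = 0.5 and the more precise above it.

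**Step 3. What change means if the first reading follows the agent.**

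Suppose the injection response is identical in the two arms, and the agents shift the first reading by an assumed 0.5 SD relative to each other.

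- If the shift persists unchanged to the second reading, the change contrast is 0 and the test rejects in about 5% of trials.
- If the shift has faded by the second reading, the change contrast is 0.5 SD in size. Its standardised value is 0.5 / √[2(1 − r)] = 0.42, 0.50, 0.65, 0.79. With 21 per arm the test then rejects in about 27%, 35%, 53% and 71% of trials.

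So change from a post-agent reading isolates the injection response only if the agent's effect on HR stays constant between readings. The documents do not address that.

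**The case against.** The strongest reply is that the timing is less open than it looks. The wording about reading immediately before the injection applies to every participant, EC children included, and the objective concerns changes during administration of the local anesthetic. A reading taken before the gel would be at least 90 s early. On that literal reading, change is intended, section H already offers a valid two-sample test for it, and one defining sentence is all that is missing. Much of this stands: the wording does favour a post-agent reading, and a test on change needs no ANCOVA to be valid. But the narrated order, including the description of the later reading as the second, points the other way, and nothing in the available text settles it.

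It is also fair that r is assumed, that the gain is modest at r of 0.7 to 0.8, and that an ANCOVA rule needs a route for non-normal data, since section H chooses its tests by normality. The fix supplies that route.

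Three stronger readings are tempting and are not supported:

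- *The planned HR test is biased or inflates false positives.* Leaving out a baseline covariate does not bias a randomised comparison. ANCOVA on a post-agent reading can reject too often when the agents shift that reading, but the plan proposes no ANCOVA, so this is a caution about the remedy.
- *Change from a post-agent reading reflects the injection only.* Step 3 shows that this depends on the agent's effect persisting unchanged.
- *Only one HR value will be stored, because Appendix I shows one H.R column.* Sub-columns may have been lost in extraction, so this supports a check and nothing more.

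**Conclusion.** The point holds as a minor, secondary one. The HR subsection disagrees with itself on whether the first reading precedes the topical agent and narrates the BC steps only. Section H does not say which HR quantity is compared and plans no adjustment.

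The cost of leaving it is an open choice of analysis and, if the reading is a true baseline, lost precision. Using change gives up between about a third of the attainable variance reduction case (r = 0.3, ratio 0.67) and less than a tenth (r = 0.8, ratio 0.92). These figures rest on assumed correlations, equal SDs and 21 per arm, and they apply only to a pre-agent reading. HR is not the outcome used for sizing, so the main comparison is untouched. Fig 1, whose legend lists HR, is not shown and may settle the timing. If it does, the missing definition and the unadjusted analysis in section H remain.

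**What to change.** 1. Reconcile the HR subsection so that the first reading is at one stated point, the same in both arms and written into both the EC and BC steps. Before the topical agent is preferable, because the reading is then a true baseline.

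2. If it is before the agent, add to section H: *HR-post will be compared between arms by ANCOVA with arm and HR-pre, reported as an adjusted difference in bpm with 95% CI; change is shown descriptively. A rank-based version will be used if residuals are clearly non-normal.*

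3. If it stays after the agent, name change (post minus pre) as the HR quantity and label the first reading post-randomisation. State that the contrast may mix the injection response with any HR effect of the agent that changes between readings. Do not claim that it reflects the injection only, and do not call an ANCOVA on that reading baseline-adjusted.

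4. Check that Appendix I has a field for each reading.

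The cost is a sentence on timing, one or two in section H, and a look at the data sheet. No extra child, reading or equipment is needed. Under option 3 the baseline-adjustment gain is given up.
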